Visit 1 and Visit 2: Visit 1 is planned 12 months (Year 1) after the parent study last visit and Visit 2 is planned 24 months (Year 2) after the parent study last visit. The visits should be planned as close to the yearly date as possible, but as a maximum, fall within a window of ± 30 days. Visit 1 and 2 are planned relative to parent study last visit; therefore, participants with a gap period between the parent study last visit and extension Baseline will have less than 12 months between the extension Baseline and Visit 1 and less than 24 months between extension Baseline and Visit 2.

Early Withdrawal: In the event of early discontinuation from the extension study, the participants will be invited for an Early Withdrawal visit as soon as possible. Visit schedules for efficacy and safety assessments are detailed in the Schedule of Activities (Section 1.3). In case the participant is not willing or cannot return to the site for the Early Withdrawal visit, a telephone call will be organized to obtain the reason for withdrawal and AEs reporting.

Unscheduled visits: A participant may return for an unscheduled visit at the discretion of the Investigator and these visits may include assessments as described in the Schedule of Activities (Section 1.3). If a participant experiences a relapse requiring treatment with steroids or switching to other DMD, a blood sample will be taken before administration of these drugs, irrespective of

time left for the next scheduled visit and blood sample collection, and irrespective of participant continuing or discontinuing the study. Further assessments and management of relapse are at the discretion of the physician.

The data from scheduled and unscheduled visits will be collected in the electronic case report form (eCRF). The schema and visit schedules for efficacy and safety assessments are detailed in the study schema (Section 1.2) and the Schedule of Activities (Section 1.3).

The planned study duration for each participant is 2 years (see Section 1.2). The study aims to enroll the first patients in Q1 2021 and have the Last Patient Last Visit in Q4 2023.

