7.2 Participant Discontinuation/Withdrawal from the Study

- A participant may withdraw from the study at any time, at his/her own request or may be withdrawn at any time at the discretion of the Investigator for safety, behavioral, compliance, or administrative reasons.
- A participant will be withdrawn from the study if the participant enrolls in another study.
- At the time of discontinuing from the study, if possible, a discontinuation visit will be conducted, as listed in the Schedule of Activities (Section 1.3). The Schedule of Activities specifies the data to collect at study discontinuation and follow-up, and any additional evaluations that need to be completed. If a physical visit is not possible, a telephone call option is provided, to obtain a reason for discontinuation and the safety assessment.
- If the participant withdraws consent for future involvement in the study, any data collected up to that point may still be used, but no future data can be generated, and any biological samples collected will be destroyed, unless the Investigator obtains permission to retain and further evaluate the samples.
- A participant has the right at any time to request destruction of any biological samples taken. The investigator will document this in the site study records.
- Participants who are discontinued/withdrawn from the study will not be replaced.
- The Investigator will secure the safety of the study participants and make every attempt to collect data.

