8.1.3 Relapses

In this protocol, symptoms and signs of relapse or worsening of MS since the previous visit will usually be captured in the context of the efficacy assessment and recorded on the relapse module of the eCRF. Therefore, symptoms, relapses or worsening of MS will not be considered as adverse events (AEs) nor captured on the AE module of the eCRF unless considered possibly or probably related to cladribine tablets (i.e. worsening is not consistent with the anticipated natural progression of the disease).

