9.6 Study Period

Study Periods

The following study periods are defined:

Treatment Period (i.e., Parent Study Period): see MAGNIFY MS IAP version 3.0 for definition.

Course 1 Treatment Period: see MAGNIFY MS IAP version 3.0 for definition.

Course 2 Treatment Period: see MAGNIFY MS IAP version 3.0 for definition.

Gap Period:

- Start = Visit end date of M24 Visit + 1
- End = Extension Study Baseline Visit start date

Year 3 Visit Period:

- Start = Visit end date of M24 Visit + 1
- End = Visit end date of M36 Visit

Year 4 Visit Period:

- Start = Visit end date of M36 Visit + 1
- End = Visit end date of M48 Visit

Year 3 Visit and Year 4 Visit Period (i.e., **Extension Study Period**):

- Start = Visit end date of M24 Visit + 1
- End = Visit end date of M48 Visit

After start of study medication until end of Year 3 Visit Period:

- Start = Start of study medication (see MAGNIFY MS IAP version 3.0 for definition)
- End = Visit end date of M36 Visit

After start of study medication until end of Year 4 Visit Period (i.e., **Parent and Extension Study Period**):

- Start = Start of study medication (see MAGNIFY MS IAP version 3.0 for definition)
- End = Visit end date of M48 Visit

In case of missing M48 Visit or early discontinuation before an End of Period defined above, the Visit end date of EW Visit will be used to replace the corresponding End date, or the study discontinuation date will be used if the EW visit was not performed.

In case of missing M36 Visit, the Visit end date of M36 Visit in the above definitions (including Start and End) will be replaced by MAGNIFY MS M24 Visit date + 480 days (which is obtained by 360 (12 months) + 90 (3 months delay allowed for FAS) + 30 (Visit window)), or the Visit end date of EW Visit if earlier, or date of discontinuation if earlier and the EW Visit was not performed.

Study Periods for MRI Assessments

The MRI scans in the parent study were reconciled during central MRI review process. Therefore, MRIs were considered as Baseline MRIs if assigned to the Baseline Visit by the central imaging review.

The following study periods for MRI assessments are defined as per MAGNIFY MS IAP version 3.0 with extension to Month 36 Visit and Month 48 Visit MRI scans:

Baseline Period (p₀): The Baseline Period is defined as the Period between the Screening and the Baseline MRI scan in MAGNIFY MS trial.

Post-Baseline Periods (ppost-Baseline):

Yearly Periods:

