14.1.1 Primary Objective: Derivation and analysis of the primary endpoint

No Evidence of Disease activity (NEDA), also referred to as freedom from disease activity, is a new goal that is emerging in MS treatment. NEDA is a composite measure of disease activity, including relapses, cognition and disability progression, and MRI activity.

NEDA-3 during the Extension Study Period is defined as absence of the following three events during the Period:

- Qualifying Relapses
- 6-months Confirmed Disability Progression (6MCDP, see definition below)
- MRI Activity (i.e., presence of T1 Gd+ lesions and/or active T2 lesions)

NEDA-3 will be analyzed with the Kaplan-Meier (KM) time-to-event method to reduce the impact of unknown/missing information.

The start date will be the end date of M24 Visit + 1.

The event date will be defined as the minimum of

- the onset date of the first qualifying relapses during the Extension Study Period
- the start date of the first 6MCDP during the Extension Study Period (see definition below)
- the scan date of the first MRI during the Extension Study Period where at least one T1 Gd+ lesion or at least one active T2 lesion (see Section 9.8 for definition) is identified.

Imputation of partial onset dates of relapses is described in Section 9.7. Since full dates of MRI scan and EDSS assessment are mandatory, partial dates of 6MCDP, or MRI Activity are not expected.

If the participant did not experience any of the three events described above during the Extension Study Period, the minimum of the scan date of the last available MRI, the assessment date of the last available EDSS, and the Extension Study completion/discontinuation date will be used as the censoring date.

The time to disease activity (in months) will be calculated as [event date or censoring date as applicable – start date + 1]/30.4375. The number of participants at risk, failed, and survival rate (i.e., the proportion of participants with NEDA-3) along with the 95% CI will be estimated as per the KM method and reported at 6-months intervals. The KM survival curve will be plotted as well.

A descriptive summary of number and proportion of participants with event (overall and by type of event, i.e., qualifying relapse, 6MCDP, or MRI activity as the earliest event) and censored will be also presented.

6MCDP

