 - Censoring date: participants with no active T2 lesion identified at any scans during the Extension Study Period will be censored at the scan date of the last available MRI during this Period
- first new T1 Gd+ lesion
 - Event date: the scan date of the first MRI during the Extension Study Period where at least one new T1 Gd+ lesion (see Section 9.8 for definition) is identified
 - Censoring date: participants with no new T1 Gd+ lesion identified at any scans during the Extension Study Period will be censored at the scan date of the last available MRI during this Period
- first 6MCDP, as measured by EDSS
 - Event date: the start date of the first 6MCDP during the Extension Study Period (see definition in Section 14.1.1)
 - Censoring date: participants with no 6MCDP started during the Extension Study Period will be censored at the assessment date of the last available EDSS during this Period
- first qualifying relapse
 - Event date: the onset date of the first qualifying relapse during the Extension Study Period
 - Censoring date: participants with no qualifying relapse reported during the Extension Study Period will be censored at the Extension Study completion/discontinuation date
- treatment start with other DMDs

- Event date: the start date of the first other DMDs used during the Extension Study Period
- Censoring date: participants who did not use any other DMDs during the Extension Study Period will be censored at the Extension Study completion/discontinuation date

A recurrent event analysis will be performed on all qualifying relapses using the Mean Cumulative Function (MCF) method, where MCF(t) represents the mean cumulative number of relapses up to time t. The MCF estimate for recurrent events will be calculated and plotted for all qualifying relapses. The MCF Nelson estimates will be presented for every month along with their 95% CIs. The increase in MCF in each month, defined as MCF(t) - MCF(t-1) will also be displayed.

Time (in months) from the initial dose of cladribine tablets (i.e. start date = date of Day 1 as defined in Section 9.5) to each event and to censoring (as defined below) will be calculated as [event date or censoring date – start date + 1/30.4375, and analyzed using the MCF method.

- recurrent qualifying relapse
 - Event date: the onset date of each qualifying relapse during the Parent and Extension Study Period

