Secondary (FAS by subgroup "Previous treatment with DMDs")	Time to event: [event date – start date + 1]/30.4375 for each qualifying relapse reported during the Parent and Extension Study Period and [censoring date – start date + 1]/30.4375 with censoring at Extension Study completion/discontinuation date for all participants	The MCF estimate for recurrent events will be calculated and plotted for all qualifying relapses. The MCF Nelson estimates will be presented for every month along with their 95% CIs. The increase in MCF in each month, defined as MCF(t) - MCF(t-1) will also be displayed.	
Secondary e with other D	endpoint: Time from M24 Visit to M MDs	RI activities, 6MCDP, qualifying	relapse, and treatment start
Secondary (FAS)	Time to event: [event date or censoring date as applicable – start date + 1]/30.4375 for first	Same as in Section 14.2.2	Same as in Section 14.2.2
Secondary (FAS by subgroup "Previous treatment with DMDs")	active T2 lesion identified during the Extension Study Period		
Secondary (FAS)	Time to event: [event date or censoring date as applicable – start date + 1]/30.4375 for first T1		
Secondary (FAS by subgroup "Previous treatment with DMDs")	Gd+ lesion identified during the Extension Study Period		
Secondary (FAS)	Time to event: [event date or censoring date as applicable – start date + 1]/30.4375 for first		
Secondary (FAS by subgroup "Previous treatment with DMDs")	6MCDP started during the Extension Study Period		
Secondary (FAS)			

Analysis (Analysis Set)	Derivation	Statistical Analysis Methods	Missing data handling
Secondary (FAS by subgroup "Previous treatment with DMDs")	Time to event: [event date or censoring date as applicable – start date + 1]/30.4375 for first qualifying relapse reported during the Parent and Extension Study Period		
Secondary (FAS)	Time to event: [event date or censoring date as applicable – start date + 1]/30.4375 for other		
Secondary (FAS by subgroup "Previous treatment with DMDs")	DMDs started during the Extension Study Period		
Secondary (FAS)	Time to event: [event date – start date + 1]/30.4375 for each qualifying relapse reported during the	The MCF estimate for recurrent events will be calculated and plotted for all qualifying relapses. The MCF	Same as Section 14.2.2

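### The telephone call that replaces a missed Early Withdrawal visit does not ask about relapse or a new DMD, yet three secondary analyses keep the participant at risk and event-free to the discontinuation date

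*Protocol*

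**What the plan says.** **What is collected.** Protocol 4.1 states that, if the participant will not or cannot come back, "a telephone call will be organized to obtain the reason for withdrawal and AEs reporting". Protocol 7.2 gives the same content: "a telephone call option is provided, to obtain a reason for discontinuation and the safety assessment". Neither mentions relapse or medication. Protocol 8.1.3 states that "symptoms, relapses or worsening of MS will not be considered as adverse events (AEs) nor captured on the AE module of the eCRF", with an exception for events considered related to cladribine. In the Schedule of Activities (Protocol 1.3), relapse reporting, concomitant medication and diary review belong to visits. The scheduled visits fall 12 and 24 months after the last parent-study visit, each ± 30 days.

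**What is analysed.** SAP 9.6 closes the study period at the Early Withdrawal visit, "or the study discontinuation date will be used if the EW visit was not performed". For analyses starting at the M24 Visit, SAP 14.2.3 then specifies:
- first relapse: "participants with no qualifying relapse reported during the Extension Study Period will be censored at the Extension Study completion/discontinuation date"
- other DMD: "participants who did not use any other DMDs during the Extension Study Period will be censored at the Extension Study completion/discontinuation date"
- recurrent relapses (MCF): "with censoring at Extension Study completion/discontinuation date for all participants"

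The relapse analyses that start at the initial dose use the same censoring date.

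**What differs elsewhere.** SAP 14.1.1 censors primary NEDA-3 at the "minimum of the scan date of the last available MRI, the assessment date of the last available EDSS" and the completion/discontinuation date. SAP 14.2.2 does the same for time to first disease activity. The descriptive relapse rule in SAP 14.1.1 scores No only when the extension period was completed. A leaver with no reported relapse is Unknown.

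**The concern.** For a leaver reached only by telephone, the time between the last visit and the discontinuation date has had no active enquiry about relapse or DMD start. The Kaplan-Meier and MCF analyses still count that time as observed and event-free. Any event in it that nobody reports is lost from the numerator, while its person-time stays in the denominator.

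Participants who leave because of new disease activity, or to change drug, are plausibly the ones with events in that interval. The error from unreported events under this rule runs one way: it overstates freedom from relapse and from other DMDs, and understates the relapse MCF. In a single-arm study there is no comparator in which such an error could cancel. The SAP also gives the same participant two statuses, Unknown in one table and at risk without relapse in another analysis.

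**Working it through.** The plan has no figure to reproduce: no hypothesis is tested, the sample-size section is blacked out, and no withdrawal, relapse or telephone-only rate is given. The text was checked first, and the size was then illustrated under stated assumptions.

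**1. Text check for a telephone-only leaver with no reported event**

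| Analysis | Treatment of time after the last visit |
|---|---|
| Primary NEDA-3 (SAP 14.1.1) | not credited beyond last MRI or EDSS |
| Time to first disease activity (14.2.2) | not credited beyond last MRI or EDSS |
| Descriptive relapse status (14.1.1) | Unknown |
| First relapse, other DMD, relapse MCF (14.2.3) | credited to discontinuation date |

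**2. Equal risk in leavers and stayers, all leavers by telephone only**

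The only relevant planning figures are 256 enrolled for 200 to 220 evaluable (Protocol 1.1): 1 − 220/256 = 14.1% and 1 − 200/256 = 21.9%. These serve as illustrative withdrawal shares w. The protocol does not say that non-evaluable means withdrawn.

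Assume that leaving times are uniform over 24 months, the last enquiry was at M24 or M36, and no later event is reported. A leaver then has on average 12 months of follow-up, 6 of them without enquiry. The unasked share of person-time is s = 6w / [24(1 − w) + 12w].
- w = 14%: 0.84 / 22.32 = 3.8%
- w = 22%: 1.32 / 21.36 = 6.2%

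With annual relapse probability p, true 24-month freedom is (1 − p)². With H = −2 ln(1 − p), the current rule gives approximately exp[−H(1 − s)]. A Kaplan-Meier simulation with 1,000,000 participants per setting agrees with this approximation:

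| p | True | w = 14%: approximation / simulated | w = 22%: approximation / simulated |
|---|---|---|---|
| 5% | 90.25% | 90.60 / 90.65 | 90.82 / 90.83 |
| 10% | 81.00% | 81.64 / 81.60 | 82.06 / 82.11 |
| 20% | 64.00% | 65.08 / 65.20 | 65.79 / 65.86 |

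The largest overstatement is 65.86 − 64.00 = 1.9 points. If half of the later events are reported spontaneously, the error is roughly halved. If all are reported, it is nil.

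**3. Higher risk in leavers, half of them by telephone only, nothing reported after the last visit**

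The hazards per year are assumed. The reference is the Kaplan-Meier estimate with every event known (2,000,000 participants per setting).

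| Stayers / leavers | w | Event proportion understated, current rule | Understated, censoring at last enquiry |
|---|---|---|---|
| 0.10 / 0.40 (relapse) | 14% | 0.98 points | 0.66 |
| 0.10 / 0.40 | 22% | 1.59 | 1.03 |
| 0.06 / 0.60 (DMD) | 14% | 1.30 | 1.07 |
| 0.06 / 0.60 | 22% | 2.08 | 1.64 |

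Changing the rule removes (0.98 − 0.66)/0.98 = 33% of the error in the first row and (1.30 − 1.07)/1.30 = 18% in the third.

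**4. Is censoring at the last enquiry a clean replacement?**

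With equal hazards, half of leavers by telephone, and every event reported spontaneously, the current rule is unbiased. The alternative overstates events by 0.3 to 0.5 points, because it counts reported events but cuts the event-free time. With half of the events reported, the two rules err by about the same amount in opposite directions. With none reported, the alternative is unbiased.

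**The case against.** The strongest reply is that relapse capture in this protocol is event-driven, not yearly. Participants are told to contact the physician at once, and a neurological examination follows within 7 days once fever or infection is excluded (8.1.3.2). Unscheduled visits include relapse and medication reporting (1.3). A relapse needing steroids or a DMD switch triggers a blood sample whether or not the participant stays in the study (4.1). Concomitant therapies are recorded to study completion (6.5), and the investigator is to make every attempt to collect data (7.2). An open-ended AE question may also elicit a relapse, even though it is recorded on another module. All of this stands, and it is why the lower end of the range is nil. It does not put either question on the call, and it depends on people who are disengaging.

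A second reply is that differing censoring rules are defensible: MRI and EDSS status is known only on assessment dates, whereas relapses and DMD starts are dated events that can be reported between visits. This also stands. It does not explain why the same leaver is Unknown in the descriptive table.

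Three stronger readings are tempting but not supported:
- **The lost-to-follow-up date.** A reader might infer that it falls after the unanswered calls and letter. Protocol 7.3 lists the contact attempts but does not define that date.
- **The size.** If every leaver went by telephone only and reported nothing, the hazards in step 3 give 2.0 to 4.3 points. Nothing in the documents supports that combination.
- **The remedy.** A reader might conclude that censoring at the last enquiry removes the bias. Step 4 shows that this needs equal hazards and no spontaneous reporting.

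**Conclusion.** The gap is real and limited in scope. It concerns time to first qualifying relapse, time to other DMD and the relapse MCF, all secondary analyses in an exploratory study. A reader might carry it over to the primary result, but the different NEDA-3 censoring rule does not credit the unasked time.

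The direction favours long-term effectiveness. The size lies between nil and roughly 1–2 percentage points at 24 months. The upper end assumes 14–22% withdrawal, half of leavers by telephone only, hazards four to ten times higher in leavers, and no spontaneous reporting. None of these rates comes from the documents. The correction is cheap and worth making.

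**What to change.** 1. **Protocol 4.1 and 7.2.** Add two items to the call: any suspected relapse and any DMD started since the last contact, each as yes/no/unknown with a date. Record them on the relapse and concomitant-medication eCRF pages. A relapse reported by telephone without examination lacks the objective impairment required in 8.1.3.1, so list it, and count it as an event only in a sensitivity analysis.

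2. **SAP 14.2.3.** Keep the current censoring rule. Add a sensitivity analysis for the three endpoints that censors at the last contact at which relapse and DMD status were obtained. Neither rule is unbiased under partial spontaneous reporting, so both should be shown.

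The cost is two or three questions on a call already planned, and one extra analysis. SAP version 2.0 is dated 05 Oct 2023 and the last visit was aimed for Q4 2023, so new questions added that late would reach few participants. The sensitivity analysis does not depend on them, because it can use the last visit with relapse and medication reporting.

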4.2 Scientific Rationale for Study Design

The purpose of this study is to explore the long-term effectiveness of cladribine tablets, in terms of disease activity and safety, in patients with highly-active RMS previously participating in the MAGNIFY MS trial.

While clinical studies have demonstrated evidence for the efficacy of new therapies for MS, these studies are often of a limited duration and may not capture long-term outcomes (Lucchetta 2020). Long-term studies are needed to establish the clinical benefits and safety of new drugs in MS patients. This extension study of the MAGNIFY MS trial will contribute to the knowledge on the long-term effect of cladribine tablets for the third and fourth year after initiation of treatment.

[figure not shown]
Treatment with cladribine tablets has a maximum duration of 20 days in 2 years, after which patients are monitored for an additional 2 years (treatment-free). The design of this study is based on visits that are part of routine clinical practice.

Significant differences in freedom from disease activity between the cladribine and placebo groups have been previously noted as early as 24 weeks. About two-thirds of patients treated with cladribine who were free from disease activity at 24 weeks after initiating treatment, and more than 80% of patients treated with cladribine who were free from disease activity at 48 weeks, remained free from disease activity at 96 weeks. This suggests that freedom from

disease activity at these earlier timepoints (before retreatment with cladribine tablets starting at Week 48) is a good predictor of freedom from disease activity at the end of the study; however, by its nature, this type of analysis enriches for a responder population (Giovannoni 2011). The current extension study will evaluate the long-term effects of cladribine tablets on freedom from disease activity.

The MRI is a sensitive, non-invasive approach to imaging the brain and spinal cord and is the preferred method of imaging to diagnose and monitor MS. The MRI based measures are of paramount relevance due to their sensitivity in detecting and quantifying the focal and diffuse pathology occurring in MS. The MRI measures of white matter lesional activity (i.e., new/enlarging T2 lesions or Gd+ T1 lesions) and those of brain atrophy (i.e., percentage of brain volume change) have shown to be valid surrogate endpoints for clinical outcomes (Sormani 2014).

In the present extension study, the long-term disease activity will be defined by no evidence of disease activity (NEDA), also referred to as freedom from disease activity. This is a new goal that is emerging in MS treatment, especially for patients with relapsing disease. It is a composite of assessments of disability and MRI. Besides long-term disease activity, the extension study will provide further information regarding the long-term safety of cladribine tablets in highly-active RMS patients.

